8.2 SAMPLE SIZE DETERMINATION

Hypothesis 1: AWEI (any combination) will have a significantly higher recruitment yield than the basic AMPLIFY recruitment strategy (no AWEI control group).

With a minimum of 1,600 in the AWEI intervention group, and 400 in the no AWEI control group, a two-sided chi-square test (for unequal sample sizes), and a 5% significance level, we will have > 95% power to detect a statistically significant difference in recruitment yield of 10% vs. 20%.

Hypothesis 2 - Delivery channel: AWEI-Research Educator will have a significantly higher recruitment yield than AWEI-brochure

Hypothesis 3 - Information emphasis: Education content with study-specific emphasis will have a significantly higher recruitment yield than with research general emphasis

Hypothesis 4 - Perspective: Education content delivered from the survivor perspective will have a significantly higher recruitment yield than education content delivered from the researcher perspective.

For these hypotheses, with a minimum of 800 per group, a two-sided chi-square test, and a 5% significance level, we will have > 95% power to detect a statistically significant difference in recruitment yield of 10% vs. 20%.

Hypothesis 5: AWEI-Research Educator with study-specific emphasis and cancer survivor perspective (combination #3, Table 1) will be the most efficacious.

The same sample size calculation applies to the comparison of any two combinations. With a minimum of 200 per group, a two-sided chi-square test, and a 5% significance level, we will have 80% power to detect a statistically significant difference in recruitment yield of 10% vs. 20%.

Calculations were performed using nQuery Advisor + nTerim, version 3.0.

Thus, the trial is fully powered with a sample of 2,000 survivors, 200 in each AWEI combination, and 400 in the no AWEI arm. However, we will randomize all survivors identified from the cancer registries. If these are less than 2000, we will expand to other

cancer registries (estimated numbers from these registries exceed 2000 survivors). If these are more than 2000, we will randomize all.

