3 STUDY DESIGN

3.1 OVERALL DESIGN

This is a prospective interventional study using a randomized factorial trial design. Participants will be randomized to one of 8 combinations of the AWEI intervention or to the control group (no AWEI) (Table 1). The AWEI intervention varies by type of delivery channel (Research Educator [RE] and Brochure), information emphasis (research general information vs. AMPLIFI study specific information), and type of perspective (information presented from a researcher or a survivor perspective).

Table 1: AWEI study design and randomized control trial (RCT) arms

	Features			AWEI combination
	Delivery channel	Information emphasis	Perspective	
Awareness Enhancing Interventions (AWEI)	Research Educator	Research general	Researcher	1
			Survivor	2
		Study specific	Researcher	3
			Survivor	4
	Brochure	Research general	Researcher	5
			Survivor	6
		Study specific	Researcher	7
			Survivor	8
No AWEI	--	--	--	

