5.1.2 DOSING AND ADMINISTRATION

In the AWEI-Research Educator (RE) arm, one of four REs attempted to contact survivors by phone starting 5 days after the letter was sent (7 attempts over 10 days) and deliver the content of the intervention following a script. Each RE was trained on the

script of one of the AWEI-RE combinations differing by Information Emphasis and Perspective to avoid contamination across AWEI groups. If the survivor did not receive the recruitment letter, the RE would give more information about the purpose of the call and offer to resend the letter.

In the AWEI-Brochure arm, one of 4 brochures according to AWEI combination was sent 4 days after the recruitment letter was sent. The same content was delivered in the AWEI-RE and AWEI-Brochure arms.

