5.2 MEASURES TO MINIMIZE BIAS: RANDOMIZATION

All participants were randomized to the AWEI (the intervention group) and no AWEI (control group) using permuted block randomization. Those who were randomized to the AWEI arm were simultaneously randomized to one of 8 combinations using the same method (Table 1).

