8.3 STATISTICAL ANALYSES

8.3.1 GENERAL APPROACH

An intent-to-treat approach is used for statistical analyses. Descriptive statistics, including frequencies and proportions, are obtained for study variables. Differences between the group and sub-group proportions are examined using the chi-square test; if the assumptions for the chi-square test are not satisfied, Fisher's exact test is used. Logistic regression compared outcomes for three groups: Control, AWEI Brochure and AWEI Research Educator. Future analyses will include logistic regression analysis to test hypotheses 3, 4, and 5. Odds ratios and their corresponding 95% confidence intervals are obtained. Statistical tests are two-sided, and a significance level of 0.05 is assumed for all tests.

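### Hypothesis 5 describes combination 4 of Table 1 in words but cites combination 3, the researcher-perspective arm

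*Combined protocol and SAP*

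**What the plan says.** Section 8.2 gives Hypothesis 5 as "AWEI-Research Educator with study-specific emphasis and cancer survivor perspective (combination #3, Table 1) will be the most efficacious". The parenthesis sends the reader to Table 1 in section 3.1, which numbers the eight AWEI arms. Within the Research Educator block, Table 1 has the row "Study specific Researcher 3", and the row directly below it, in the same channel and emphasis, is the survivor perspective, numbered 4.

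Section 5.2 uses the same table for allocation: survivors assigned to AWEI "were simultaneously randomized to one of 8 combinations using the same method (Table 1").

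Section 8.2 also sets the direction for each factor. Hypothesis 2 favours the Research Educator over the brochure, Hypothesis 3 favours study-specific over general emphasis, and Hypothesis 4 reads "Education content delivered from the survivor perspective will have a significantly higher recruitment yield than education content delivered from the researcher perspective".

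On the analysis, section 8.3.1 says "Future analyses will include logistic regression analysis to test hypotheses 3, 4, and 5", with no arm or contrast for Hypothesis 5. Section 8.3.2 sets out comparisons for Hypotheses 1 and 2 only.

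**The concern.** One sentence identifies the target arm of a prespecified hypothesis in two ways, and the two do not agree. No other section names the arm, so nothing later in the document settles which is meant.

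The number is a reference to the table that also defines the randomized combinations, so it could plausibly be carried into an analysis program as an arm code. If it were, the arm singled out as the expected best would be the researcher-perspective arm, the opposite of what the words say and of what Hypothesis 4 predicts.

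The two arms also differ in delivery. Section 5.1.2 says each educator was trained on the "script of one of the AWEI-RE combinations differing by Information Emphasis and Perspective to avoid contamination across AWEI groups", so combinations 3 and 4 have different scripts and, on the natural reading, different educators.

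Because the Hypothesis 5 analysis is described as still to come, an ambiguous target arm also leaves room for a later question about whether the arm was settled after results were seen.

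**Working it through.** **Step 1. Rebuild the numbering of Table 1 (section 3.1).** The Research Educator block opens with "Research Educator Research general Researcher 1" and the brochure block with "Brochure Research general Researcher 5". Reading down the rows:

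| Combination | Channel | Emphasis | Perspective |
|---|---|---|---|
| 1 | Research Educator | General | Researcher |
| 2 | Research Educator | General | Survivor |
| 3 | Research Educator | Study specific | Researcher |
| 4 | Research Educator | Study specific | Survivor |
| 5 | Brochure | General | Researcher |
| 6 | Brochure | General | Survivor |
| 7 | Brochure | Study specific | Researcher |
| 8 | Brochure | Study specific | Survivor |

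**Step 2. Match the words of Hypothesis 5 to the rows.**

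| Factor | Hypothesis 5 in words | Combination 3 | Combination 4 |
|---|---|---|---|
| Channel | Research Educator | match | match |
| Emphasis | Study specific | match | match |
| Perspective | Survivor | no match | match |
| Total | | 2 of 3 | 3 of 3 |

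**Step 3. Rule out a table-reading artefact.** The numbers run from 1 to 8 in order, and the researcher row comes before the survivor row in all four pairs, so every odd number is a researcher arm. No realignment of the merged cells makes combination 3 a survivor arm.

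**Step 4. Ask which half is more likely wrong.** The favoured levels in Hypotheses 2, 3 and 4 are Research Educator, study specific and survivor. The Hypothesis 5 wording is those three levels combined. Combination 3 would keep the first two and reverse the third. This points to the number as the slip; it is an inference, not a statement in the document.

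**Step 5. Check whether any figure depends on the number.** Section 8.2 gives 80% power for comparing any pair of combinations, with 200 per arm, 10% versus 20%, two-sided 5%. With the usual pooled-variance normal approximation (no continuity correction):

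- average proportion = (0.10 + 0.20)/2 = 0.15
- null term = 1.96 × √(2 × 0.15 × 0.85) = 1.96 × 0.505 = 0.990
- alternative term = √(0.10 × 0.90 + 0.20 × 0.80) = √0.25 = 0.50
- power = Φ[(0.10 × √200 − 0.990)/0.50] = Φ[(1.414 − 0.990)/0.50] = Φ(0.849) = 80.2%
- n for 80% power = [(0.990 + 0.842 × 0.50)/0.10]² ≈ 199 per arm

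The stated 80% is reproduced. Every combination has the same planned 200, so the result is the same whether the target is combination 3 or 4. This check takes all 200 as the denominator, as section 8.2 does. It shows only that the power statement does not depend on the combination number; it does not validate that denominator for the primary endpoint, which section 8.1 defines among survivors screened and found eligible.

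**The case against.** The strongest reply is that the consequence is close to nil. The sentence spells out all three factor levels beside the number, and the three preceding hypotheses favour the same levels, so a careful reader will reach combination 4. The plan states no contrast for Hypothesis 5. If the eventual model estimates all eight combinations, the label changes no estimate, only which arm is called the hypothesized best or used as the reference. The analysis is also deferred and lies outside the comparisons in section 8.3.2.

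Most of this stands, and it is why the point is minor and the harm conditional. It does not remove the contradiction: the number is wrong against the table it cites, and which arm is declared the hypothesized best is exactly what Hypothesis 5 is about.

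Two narrower objections are also fair. Nothing in the document suggests that the actual allocation codes depart from Table 1, so an error in the table is a remote possibility; but the codes are not shown, and checking them is trivial. And section 5.1.2 does not state outright that each of the four educators had a different script. That is the natural reading of four educators, each trained on one of the combinations to prevent contamination. The difference in script follows from the design in any case.

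**Conclusion.** The concern holds as a minor internal inconsistency. The arm described in Hypothesis 5 is combination 4 of Table 1; the arm cited is combination 3. They differ on one factor of three, perspective. Sample size, power, randomization, the endpoint and Hypotheses 1 to 4 are untouched.

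The wrong arm would be singled out only if Hypothesis 5 were coded from the number rather than the words. That the number is the error is well supported by the directions of Hypotheses 2 to 4, but it assumes that the authors meant what the words say and that the allocation codes follow Table 1. The document confirms neither, so sections 3.1 and 8.2 need to be reconciled by the authors.

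**What to change.** 1. Confirm with the study team that the survivor-perspective arm is the one intended, and that the randomization and dataset codes follow the numbering of Table 1.
2. If they do, change the citation in Hypothesis 5 (section 8.2) from combination 3 to combination 4. If the codes depart from Table 1, correct the table numbering instead.
3. In either case, define the Hypothesis 5 arm in the analysis program by its factor levels (channel = Research Educator, emphasis = study specific, perspective = survivor) rather than by a combination number, and record this before the deferred analysis is run.

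The cost is a check of arm codes and a one-digit text correction, or a renumbering of the table if the codes turn out to differ. No design element changes.

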8.3 STATISTICAL ANALYSES

8.3.1 GENERAL APPROACH

An intent-to-treat approach is used for statistical analyses. Descriptive statistics, including frequencies and proportions, are obtained for study variables. Differences between the group and sub-group proportions are examined using the chi-square test; if the assumptions for the chi-square test are not satisfied, Fisher's exact test is used. Logistic regression compared outcomes for three groups: Control, AWEI Brochure and AWEI Research Educator. Future analyses will include logistic regression analysis to test hypotheses 3, 4, and 5. Odds ratios and their corresponding 95% confidence intervals are obtained. Statistical tests are two-sided, and a significance level of 0.05 is assumed for all tests.

8.3.2 ANALYSIS OF THE PRIMARY EFFICACY ENDPOINT(S)

Imbalances in randomization groups if any will be adjusted in analysis.

Outcome variables are categorical. We will use logistic regression to test for differences in outcomes across the randomized groups.

Hypothesis 1 will be tested using all randomized individuals. We will test differences in outcomes for 2 groups: AWEI (any combination) vs. no AWEI (control group).

Hypothesis 2 will be tested within the AWEI group. We will test differences in outcomes for 2 groups: AWEI-Research Educator vs. AWEI-brochure.

Exact 95% confidence intervals based on the binomial distribution will be determined for each proportion.

All statistical analyses will be conducted using SAS, version 9.4 (SAS Institute, Cary, NC).

8.3.3 ANALYSIS OF THE SECONDARY ENDPOINT(S)

We will use the same statistical approach for secondary endpoints.

8.3.4 SAFETY ANALYSES

None

8.3.5 BASELINE DESCRIPTIVE STATISTICS

We will first conduct descriptive analyses to describe the study population and verify that the randomization groups are balanced in age, gender, cancer type and stage, time since diagnosis, and rural/urban status.

9 SUPPORTING DOCUMENTATION AND OPERATIONAL CONSIDERATIONS

9.1 REGULATORY, ETHICAL, AND STUDY OVERSIGHT CONSIDERATIONS

9.1.1 INFORMED CONSENT PROCESS

9.1.1.1 CONSENT/ASSENT AND OTHER INFORMATIONAL DOCUMENTS PROVIDED TO SUBJECTS

A waiver of informed consent and documentation is approved by the IRB for this trial, given that the purpose is to test recruitment strategies before enrollment in a study (before consent to a study occurs).

9.1.1.2 CONSENT PROCEDURES AND DOCUMENTATION

Not applicable

9.1.2 STUDY DISCONTINUATION AND CLOSURE

Given this low risk there is no independent Data Safety and Monitoring Board (DSMB) for the AWEI trial, but will rely on the DSMB established for the AMPLIFI. The AMPLIFI DSMB may temporarily suspend or prematurely terminate the trial if there is sufficient reasonable cause. Written notification, documenting the reason for study suspension or termination, will be provided by the suspending or terminating party to regulatory authorities. If the study is prematurely terminated or suspended, the Principal Investigators will promptly inform the IRB, and will provide the reason(s) for the termination or suspension.

Circumstances that may warrant termination or suspension include, but are not limited to:

- Demonstration of efficacy that would warrant stopping
- Insufficient compliance to protocol requirements
- Data that are not sufficiently complete and/or evaluable
- Determination of futility

Study may resume once concerns are addressed, and satisfy the IRB.

9.1.3 CONFIDENTIALITY AND PRIVACY

Subject confidentiality and privacy is strictly held in trust by the participating investigators and their staff. Therefore, the study protocol, documentation, data, and all other information generated will be held in strict confidence. No information concerning the study or the data will be released to any unauthorized third party without prior written approval of the Principal Investigator.

All research activities will be conducted in as private a setting as possible.

IRB representatives may inspect all documents and records required to be maintained by the investigators. The clinical study site will permit access to such records.

The study subject's contact information will be securely stored for internal use during the study. At the end of the study, all records will continue to be kept in a secure location for as long a period as dictated by the reviewing IRB and/or Institutional policies.

Study subject research data, which is for purposes of statistical analysis and scientific reporting, will be stored at UAB. This will not include the subject's contact or identifying information. Rather, individual subjects and their research data will be identified by a unique study identification number. The study data entry and study management systems used by research staff will be secured and password protected.

9.1.4 QUALITY ASSURANCE AND QUALITY CONTROL

We reviewed recruitment report weekly to ensure that recruitment was done as planned. We provided ongoing training to interventionists to ensure that the intervention was delivered as planned and appropriately documented. We oversaw that the intervention was delivered as planned (e.g., brochure mailed on the prespecified schedule). We had a detailed manual of operations specifying procedures.

The site will provide direct access to all trial related sites, source data/documents, and reports for the purpose of monitoring and inspection by local and regulatory authorities.

9.1.5 DATA HANDLING AND RECORD KEEPING

9.1.5.1 DATA COLLECTION AND MANAGEMENT RESPONSIBILITIES

Data collection is the responsibility of the clinical trial staff at the site under the supervision of the Principal Investigators. The Principal Investigators are responsible for ensuring the accuracy, completeness, legibility, and timeliness of the data reported.

All source documents should be completed in a neat, legible manner to ensure accurate interpretation of data.

9.1.5.2 STUDY RECORDS RETENTION

Study documents should be retained for a minimum of 3 years after the completion of the study. These documents should be retained for a longer period, however, if required by local regulations.

9.1.6 PROTOCOL DEVIATIONS

A protocol deviation is any noncompliance with the clinical trial protocol requirements. The noncompliance may be either on the part of the subject, the investigator, or the study site staff. As a result of deviations, corrective actions are to be developed by the site and implemented promptly.

It is the responsibility of the Principal Investigator to use continuous vigilance to identify and report deviations within 10 working days of identification of the protocol deviation. Protocol deviations must be sent to the reviewing Institutional Review Board (IRB) per their policies. The

Principal Investigator is responsible for knowing and adhering to the reviewing IRB requirements.

9.1.7 CONFLICT OF INTEREST POLICY

The independence of this study from any actual or perceived influence is critical. Therefore, any actual conflict of interest of persons who have a role in the design, conduct, analysis, publication, or any aspect of this trial will be disclosed and managed. Furthermore, persons who have a perceived conflict of interest will be required to have such conflicts managed in a way that is appropriate to their participation in the design and conduct of this trial.

9.2 ABBREVIATIONS

AE	Adverse Event
ANCOVA	Analysis of Covariance
CFR	Code of Federal Regulations
CONSORT	Consolidated Standards of Reporting Trials
CRF	Case Report Form
DHHS	Department of Health and Human Services
GCP	Good Clinical Practice
HIPAA	Health Insurance Portability and Accountability Act
ICH	International Conference on Harmonisation
ICMJE	International Committee of Medical Journal Editors
IRB	Institutional Review Board
LSMEANS	Least-squares Means
NCT	National Clinical Trial
NIH	National Institutes of Health
OHRP	Office for Human Research Protections
PI	Principal Investigator
QA	Quality Assurance
QC	Quality Control
SAE	Serious Adverse Event
SAP	Statistical Analysis Plan
SOA	Schedule of Activities
SOP	Standard Operating Procedure
UP	Unanticipated Problem
US	United States
